8.3 Treatment with Ribociclib

8.3.1 Drug Dispense, Administration and Treatment Regimens

8.3.1.1 Investigational drugs regimen will be provided by Novartis to the participating

The investigational drug used in the course of this trial is ribociclib in combination with standard endocrine therapy. Ribociclib in combination with any endocrine regimen will be provided by Novartis to the participating sites in the study and will be dispensed by the study center personnel on an outpatient basis. Endocrine therapy in this case has to be prescribed according to study settings (see TABLE 18 below).

On the first day of each cycle, patients will receive an adequate drug supply for self-administration at home. The investigator must emphasize compliance and will instruct the patient to take ribociclib and standard endocrine therapy exactly as prescribed.

8.3.1.2 Treatment arms

This is a non-randomized Phase II study.

8.3.1.3 Treatment assignment

All postmenopausal, hormone-receptor positive patients without indication to chemotherapy will be assigned to treatment with ribociclib and standard endocrine therapy.

8.3.1.4 Dispensing the study drug

In combination with any endocrine regimen ribociclib will be provided by Novartis to the participating sites in the study setting and will be dispensed by the study center personnel on an outpatient basis. All dosages prescribed to the patient and all dose changes during the study must be recorded on the Dosage Administration Record CRF.

8.3.1.5 Study drug compliance

The investigator and/or study personnel will assess compliance at each patient visit. To accurately determine the patient's drug exposure throughout the study, the following information must be reported on the Drug Administration Record CRF pages for both everolimus and standard endocrine therapy and in the source document.

- Planned dose administration
- Actual total daily dose administered
- Start and end date of drug administration
- Dose change (no or yes)
- Reason for dose change (e.g. adverse event, dosing error, lab test abnormality etc.)

8.3.1.6 Patient Compliance

Compliance with daily ribociclib is very important to the conclusions of this study. To assess treatment compliance patients are asked to present all tablets not yet used on every visit to the study site. At the end of the treatment period patients must return all unused tablets. Patients are instructed to notify the investigator of any missed doses. The investigator will make tablet counts at each patient visit during treatment. The tablet counts are to be documented in the eCRF. Dates of missed doses are also to be recorded on the eCRF.

8.3.1.7 Study drug accountability

The investigator or designee must maintain an accurate record of the shipment and dispensing of only for study drugs supplied by Novartis in a drug accountability log. The field monitor will note drug accountability during site visits and at the completion of the study. Patients will be asked to return all unused Novartis-supplied study drugs and packaging on an ongoing basis or at the time of study drug discontinuation.

8.3.1.8 Disposal and destruction

The drug supply can be destroyed at the local site. Destruction must be recorded in the local Drug Accountability Log, and will be controlled by the field monitor.

8.3.1.9 Instructions for use of study drug

All patients will receive ribociclib + standard endocrine therapy. All patients will take ribociclib orally per day. All patients will also take standard endocrine therapy once daily (dosage according to the label, see TABLE 18)

Endocrine treatment		+Ribociclib
Exemestane	25 mg/d	600 mg/d
Letrozole (Hortobagyi et al. Mona-LEEsa-2, 2016)	2,5 mg/d	600 mg/d
Anastrozole	1 mg/d	600 mg/d
Fulvestrant	500 mg/q4w	600 mg/d

Table 18: Recommended treatment regimen for combination with ribociclib

On treatment Day 1, patients will be provided or prescribed study drugs for self-administration at home. Enough tablets should be provided or prescribed to cover administration until next scheduled visit plus one week at minimum.

Ribociclib will be dosed starting on treatment Day 1 (Inclusion / Recruitment Visit). Patients will be instructed to take the ribociclib capsule(s) orally with a large glass of water once daily at the same time each day with or without food.

Exemestane / letrozole / anastrozole / fulvestrant will be dosed starting on treatment Day 1 according to the recommended daily dosage (refer to TABLE 18 above). Package insert instructions should be followed.

Patients should be instructed to take the study drug combination of ribociclib and standard endocrine therapy with a large glass of water (~250 mL) at the same time each day. Evening doses are strongly not recommended.

- Ribociclib can be administered with or without food; however dietary habits around the time of dosing should be as consistent as possible throughout the study.

- Patients should be instructed to swallow the ribociclib whole and not to chew or crush them.

- If vomiting occurs during the course of treatment, no re-dosing of the patient is allowed before the next schedule dose. The occurrence and frequency of any vomiting during a treatment cycle must be noted in the adverse events section in the eCRF.

- Any doses that are missed (not taken within 6 hours of the intended time) should be skipped and should not be replaced or made up on subsequent day.

- Patients must avoid consumption of grapefruit, grapefruit hybrids, pummelos, starfruit, Seville oranges or products containing the juice of each during the entire study and preferably 7 days before the first dose of study medications, due to potential CYP3A4 interaction with the study medications.

Note: Orange juice is allowed.

1. No herbal or dietary supplements are permitted.
2. Multivitamins are permitted.

Ribociclib and standard endocrine therapy will be taken daily from Inclusion / Recruitment Visit, Day 1 until disease progression, unacceptable toxicity, death, and withdrawal from the study for any other reason.

The End of treatment (EOT) is defined as the last date that the patient has taken the study drug ribociclib, excluding an ribociclib interruption for < 4 weeks. A Follow-up visit 4 weeks after the last date that the patient has taken the study drug will be conducted to report any adverse events during this period.

The investigator should promote compliance by instructing the patient to take the study drugs exactly as prescribed and by stating that compliance is necessary for the patient's safety and the validity of the study. The patient should be instructed to contact the investigator if she is unable for any reason to take the study drug as prescribed.

All dosages prescribed and dispensed to the patient and all dose changes during the study must be recorded on the Dosage Administration Record CRF.

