PR	Partial Response
QOL	Quality of Life
RAD001	Everolimus
RANKL	Receptor activator of nuclear factor kappa B ligand
RECIST	Response Evaluation Criteria In Solid Tumors
SAE	Serious Adverse Event
SAR	Suspected Adverse Reaction
SD	Stable Disease
SGPT	Serum Glutamic-Pyruvic Transaminase

SPC	Summary of Product Characteristics
SUSAR	Suspected Unexpected Serious Adverse Reaction
TK	Tyrosine Kinase
TNBC	Triple negative breast cancer
TTP	Time To Progression
YOB	Year of Birth

EUDRACT-NO.: 2013-001269-18	Protocol No.: D-IV
Sponsor: Universitätsklinikum Ulm (AöR), [name], [name]	
Responsible person: [name]. [name], University Hospital Ulm	
Coordinating Investigator („Leiterin der klinischen Prüfung“ acc. to German Drug Law): [name]. [name], University Hospital Düsseldorf	
Title: DETECT IV – A prospective, multicenter, open-label, phase II study in patients with HER2-negative metastatic breast cancer and persisting HER2-negative circulating tumor cells (CTCs).	
Investigational medicinal products (IMP): DIVa: Everolimus tablets 5 mg/Ribociclib capsules 3 x 200 mg /d d 1-21 q28d or DIVb: Eribulin mesylate 1.23 mg/m² d1+8 q3w	
Indication/Clinical Trial population	

Everolimus/Ribociclib cohort: Postmenopausal female patients with hormone-receptor positive, HER2-negative metastatic breast cancer with only HER2-negative circulating tumor cells (CTCs) and indication for standard endocrine therapy.
	

Eribulin cohort: Patients with hormone-receptor positive, HER2-negative metastatic breast cancer and indication to chemotherapy or patients with triple-negative metastatic breast cancer, both with only HER2-negative circulating tumor cells (CTCs).
	

Clinical Trial Design

A prospective, multicenter, open-label, phase II study.

[figure not shown]

Figure 1: Screening and Design of DETECT IV

Planned duration of the entire study

The study starts when the necessary approval has been given by the competent authority (BfArM). Furthermore the competent ethics committee must have given a favorable opinion on study conduct before the first patient is included.

The trial is terminated after the last patient has either died or completed the 24-months follow-up period.

The maximum study duration is 72 months and 3 weeks.

Planned duration of individual study participation

The individual study participation begins with the screening visit and ends when the patient has either died or completed the 24-months follow-up period.

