On the first day of each cycle, patients will receive an adequate drug supply for self-administration at home. The investigator must emphasize compliance and will instruct the patient to take ribociclib and standard endocrine therapy exactly as prescribed.

All patients will receive ribociclib + standard endocrine therapy. All patients will take ribociclib capsules orally per day (3-weeks-on/1-week-off schedule) and will also take standard endocrine therapy once daily (dosage according to the label).

Endocrine treatment		+Ribociclib
Exemestane	25 mg/d	600 mg/d*
Letrozole (Hortobagyi et. al 2016 - MonaLEEsa-2 trial)	2,5mg/d	600mg/d*
Anastrozole	1 mg/d	600mg/d*
Fulvestrant	500 mg/q4w	600mg/d*

* 1-21 d q28d

Table 2: Recommended treatment regimen for combination with ribociclib

Ribociclib will be dosed for the first 21 days out of the 28 day cycle. Patients should be instructed to take the ribociclib capsules orally with a large glass of water at the same time; however dietary habits around the time of dosing should be as consistent as possible throughout the study.

Exemestane / letrozole / anastrozole / fulvestrant will be dosed starting on treatment Day 1 according to the recommended dosage (see TABLE 2). Package insert instructions should be followed.

Ribociclib and endocrine therapy will be taken from treatment Day 1 up to 12 months or until disease progression, unacceptable toxicity, death, or withdrawal from the study for any other reason. If medically indicated ribociclib treatment may be continued during follow up.

Treatment with eribulin:

Eribulin as the ready to use solution will be dosed 1.23 mg/m² which should be administered intravenously over 2 to 5 minutes on Days 1 and 8 of every 21-day cycle. Eribulin should be given 12 months or until disease progression, unacceptable toxicity, death, or withdrawal from the study for any other reason. If medically indicated eribulin treatment may be continued during follow up.

End of treatment:

The end of treatment (EOT) is defined as the last date that the patient has taken the study drug, excluding interruption for less than 4 weeks. Maximum Treatment Period in both cohorts is 12 months. A Follow-up visit 4 weeks after the last date that the patient has taken the study drug will be conducted to report any adverse events during this period.

Treatment in Follow-Up Period:

Therapy after treatment period (i.e. treatment in the follow-up period) is at the discretion of the investigator.

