3.3.4 Clinical Safety of Ribociclib As Single Agent

As of 15-Jun-2015, 157 patients have been treated with single agent ribociclib in the first-in-human (FIH) phase I study; 85 patients have been treated in the initial dose escalation part for the 3 week on/1 week off regimen and 47 patients in the dose expansion part of the study; 18 patients were enrolled for the continuous dosing regimen with ribociclib and, 7 patients were enrolled in the liquid formulation cohort.

Patients with advanced solid tumors or lymphomas were treated with increasing doses of ribociclib orally, once daily (qd) for 21 days followed by a 1-week rest (28-day cycle). Doses ranging from 50 mg to 1200 mg were

evaluated on this schedule. Treatment has been discontinued in 120 (90%) patients; the primary reasons for treatment discontinuation were: disease progression (106 [80%] patients); adverse events (AEs) (7 [5%] patients); death (2 [1.5%] patients); withdrawal of consent (3 [2%] patient); and loss to follow up (1 [1%] patient).

The most frequently reported AEs ($\geq 10\%$), regardless of grade, causality and ribociclib dose were: nausea (52.3%); fatigue (40.9%); diarrhea (37.1%); vomiting (35.6%); neutropenia (34.1%); anemia (32.6%); decreased appetite, thrombocytopenia (23.5% each); white blood cell count decrease (22.7%); leukopenia (22%); constipation (21.2%); dyspnea (20.5%); asthenia (19.7%); cough (18.2%); hyperglycemia (17.4%); headache, hypoalbuminemia (16.7% each); ECG QT prolonged (15.9%); abdominal pain, back pain, lymphocyte count decrease, pyrexia (15.2% each); AST increase, blood creatinine increased, dizziness, lymphopenia (14.4% each); peripheral edema (13.6%); neutrophil count decreased (12.9%); ALT increase, pain in extremity (12.1% each) and hypocalcemia (11.4%).

For either continuous or intermittent dosing, the onset of neutropenia (most frequently Grade 2) occurs by Day 15, reaching a nadir in the third or fourth week with recovery during the week of drug holiday for the three weeks on/one week off schedule. Some patients require additional time for recovery (7 to 14 days). QT changes become evident in the first cycle by Day 8 and later (once steady state is reached), are associated with the maximum drug levels between 1 to 8 h post-dose, and remain stable or improve in subsequent cycles.

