- Review of the inclusion or exclusion criteria.
 - If during pre-treatment evaluation period a patient is found not to be eligible due to one of the inclusion or exclusion criteria, she is excluded from the study. Beyond the respective finding and the respective inclusion or exclusion criterion no further data need to be documented in the eCRF. Patients who are excluded from the study and who consent in additional assessment will be monitored during their course of disease as part of their routine treatment in order to gain further information about the impact of CTC detection on disease progression.
 - If the patient meets all inclusion criteria and none of the exclusion criteria, she is eligible according to section 7.0 of the protocol and for treatment according to section 8 of the protocol.
- Start of treatment according to the protocol / Dispense everolimus/ribociclib or eribulin to patients according to the treatment plan (section 8).
- Assessment of adverse events

Investigation		Time interval before re- recruitment
Blood Sampling with Screening Kit (Screening Visit) for CTC assessment	- Total number per 7,5 mL	3 weeks (Results must be available prior to IC part 2 and prior to start of Inclusion Visit)
	- HER2 status	
Hematology	- Hemoglobin - Hematocrit - Red blood cell count - Differential white blood cell count - Platelet count	7 days
Biochemistry	- Total and direct bilirubin - ALT - AST - Serum creatinine - Albumin - BUN or urea	7 days

	
 - Fasting cholesterol and triglycerides (Everolimus/ribociclib cohort only) - Fasting glucose (Everolimus cohort only) - Sodium, potassium, calcium(ribociclib-cohort only) - Potassium and Magnesium (Eribulin-cohort) 	
Pregnancy test	- (Eribulin cohort only)	7 days
Tumor evaluation (see section 10.2.1)	
 - Mandatory imaging - Other imaging as necessary to document all sites of disease - Clinical lesion status - Tumor markers (mandatory: CA15-3; optional: CEA, CA125) 	6 weeks
Cardiac investigations	- 12-lead ECG	3 weeks
Quality of life questionnaires	
 - EORTC QLQ-C30 - EORTC QLQ-BR23 	1 week

Table 12: Information on special investigations during Pre-Treatment Period

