Everolimus and standard endocrine therapy will be taken daily from Inclusion / Recruitment Visit, Day 1 until disease progression, unacceptable toxicity, death, and withdrawal from the study for any other reason.

The End of treatment (EOT) is defined as the last date that the patient has taken the study drug everolimus, excluding an everolimus interruption for < 4 weeks. A Follow-up visit 4 weeks after the last date that the patient has taken the study drug will be conducted to report any adverse events during this period.

The investigator should promote compliance by instructing the patient to take the study drugs exactly as prescribed and by stating that compliance is necessary for the patient's safety and the validity of the study. The patient should be instructed to contact the investigator if she is unable for any reason to take the study drug as prescribed.

All dosages prescribed and dispensed to the patient and all dose changes during the study must be recorded on the Dosage Administration Record CRF.

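### Section 8.3.1.9 and Table 18 give ribociclib daily with no off-week, although the synopsis sets days 1–21 of 28; the dose floor in 8.3.2.1 also contradicts Table 19

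*Protocol*

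**What the plan says.** Section 6.3 directs an eligible patient to treatment with the words "for treatment according to section 8 of the protocol", so section 8 is the text a site works from.

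- **Synopsis.** The investigational-product line reads "Ribociclib capsules 3 x 200 mg /d d 1-21 q28d". The treatment plan says "Ribociclib will be dosed for the first 21 days out of the 28 day cycle", and Table 2 carries a matching footnote. The German synopsis in Appendix I gives the same schedule in its product line and under its dosing table.
- **Section 8.3.1.9.** The patient instruction is "Patients will be instructed to take the ribociclib capsule(s) orally with a large glass of water once daily at the same time each day". The duration sentence is "Ribociclib and standard endocrine therapy will be taken daily from Inclusion / Recruitment Visit, Day 1 until disease progression". Table 18 lists 600 mg/d in all four rows with no footnote.
- **Section 8.3.1.6.** "Compliance with daily ribociclib is very important to the conclusions of this study".
- **Section 8.3.2.1.** Table 19 steps down from 600 to 400 to 200 mg/d and ends there. The sentence beneath it places the point of no further reduction at 200 mg every other day. The German synopsis gives 200 mg as the minimum daily dose.

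**The concern.** Two dosing rules for the same investigational drug stand in one protocol, and the wrong one is in the section sites are told to follow. Section 3.3.4 describes neutropenia reaching its nadir in week three or four, "with recovery during the week of drug holiday for the three weeks on/one week off schedule", with some patients needing a further 7 to 14 days. It also reports QTcF of 500 ms or more in 5.4% of patients at 600 mg. Section 3.3.9.3 reports grade 3/4 neutropenia in 59.3% of patients on ribociclib plus letrozole. Removing the off-week removes the recovery period the protocol itself describes, and grade 4 neutropenia above 20% is a stopping criterion in 13.4.

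Continuous dosing cannot be dismissed as an obvious misprint. Section 3.3.4 records 18 phase I patients on a continuous regimen, and 3.3.5 describes a breast cancer response on it.

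On the analysis side, section 15.1 defines the per-protocol set by treatment according to protocol, and 8.3.1.6 assesses compliance against daily intake. Both would be judged against the wrong schedule.

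**Working it through.** **1. Which text is wrong.** The days 1–21 schedule appears in the synopsis product line, twice in the synopsis treatment text, in the Table 2 footnote, and in both places in the German synopsis. Section 8.3 never states it: 8.3.1.1 mentions the first day of each cycle but gives no cycle length. The source of the error is visible in 8.2.1.9: "Everolimus and standard endocrine therapy will be taken daily from Inclusion / Recruitment Visit, Day 1 until disease progression". The ribociclib sentence is the same with the drug name changed. Everolimus is a continuous drug; ribociclib is not. Other carry-over confirms this: 8.3.1.5, in the ribociclib section, asks for exposure records for everolimus.

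**2. Dose per 28 days at full dose.**
- Intended: 21 × 600 mg = 12,600 mg; 21 × 3 = 63 capsules of 200 mg.
- Section 8.3.1.9 read literally: 28 × 600 mg = 16,800 mg; 28 × 3 = 84 capsules.
- Ratio: 16,800 / 12,600 = 1.33, or +33%.

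**3. Would dispensing limit it?** Section 8.3.1.9 requires supply to the next visit plus at least one week. Assume 4-weekly visits (the synopsis allows 2 to 4 weeks). On the intended schedule this is 63 + 7 × 3 = 84 capsules, exactly enough for 28 continuous days.

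**4. Compliance by capsule count.** A fully adherent three-weeks-on patient uses 63 capsules. Against daily intake she scores 63/84 = 75%. A patient who took the drug continuously scores 84/84 = 100%.

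**5. Dose floor.**
- Table 19: 200 mg/d on days 1–21 gives 21 × 200 = 4,200 mg per cycle.
- Text of 8.3.2.1: every other day gives 11 × 200 = 2,200 mg within days 1–21, or 14 × 200 = 2,800 mg over 28 days.

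The text therefore implies a third reduction step that Table 19 does not list. Table 20, for grade 2 bilirubin rises, stops ribociclib when toxicity recurs after two reductions. The everolimus section (8.2.2.1) has the same sentence with 5 mg every other day, which is a real level for that drug.

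**The case against.** The strongest reply is that only one sentence conflicts outright. Taking capsules once daily at the same time can describe how to dose on dosing days; the German synopsis uses similar wording beside its days 1–21 footnote. The 600 mg/d in Table 18 is a dose rate that lacks a footnote. The duration sentence cannot be fully literal anyway, because it also has endocrine therapy taken daily while Table 18 lists fulvestrant every four weeks. The intended schedule is recoverable from the synopsis. Patients also receive an information sheet (Appendix X), which is not in the text available for review and may state the off-week. Blood counts, ECGs and interruption rules offer protection, and capsule returns would differ: 21 of 84 on the intended schedule, none if continuous. The protocol sets no compliance threshold, so no misclassification in the per-protocol set is shown. The floor sentence is conditional and orders no one to reduce to alternate days.

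Much of this stands as a limit on the likely consequence: +33% is an upper bound and no actual overdosing is shown. It does not remove the error. Section 8.3 never states the off-week, and one sentence affirmatively denies it. The capsule count helps only if read against the right schedule; read against daily intake, no returns look like full compliance. The floor sentence still leaves a site unsure whether a patient at 200 mg/d must stop or may reduce again.

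**Conclusion.** The point holds and must be fixed on patient-safety grounds. Section 8.3.1.9 and Table 18 contradict the synopsis on the ribociclib schedule, and 8.3.2.1 contradicts Table 19 and the German synopsis on the lowest dose. The upper bound is 33% more drug per 28 days with no recovery week, for up to 90 ribociclib patients; it assumes that every site follows section 8.3 literally. How often that would happen cannot be judged from the protocol. The statistical effect is confined to compliance assessment and the supportive per-protocol set. The ITT clearance rate remains estimable, actual doses are to be recorded (8.3.1.4), and the sample-size and precision figures are unchanged.

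**What to change.** - **8.3.1.9 and Table 18:** state 600 mg/d on days 1–21 of each 28-day cycle, three weeks on and one week off. Add days 1–21 to the once-daily instruction. Rewrite the duration sentence so that ribociclib follows that schedule and endocrine therapy follows Table 18.
- **8.3.2.1:** replace 200 mg every other day with 200 mg/d, matching Table 19 and the German synopsis.
- **8.3.1.6:** remove the reference to daily ribociclib and count capsules against 63 per 28-day cycle at full dose.
- **Per-protocol set:** judge adherence against the days 1–21 schedule.
- **Sites:** notify them by amendment or clarification letter.

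The cost is about five sentences and one table footnote, with no analysis or sample-size cost.

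A separate, lower-priority inconsistency in the eribulin cohort could be settled in the same amendment: 3.5.1 recommends lipegfilgrastim with each chemotherapy cycle, while 8.5.4 bars prophylactic growth factors. The sponsor should choose one policy. The conclusion above does not depend on it.
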